7.6.2 Analysis Secondary Efficacy Endpoint

A hierarchical, closed-testing procedure will be utilized for the secondary endpoint: If the null hypothesis for the primary efficacy endpoint is rejected, the secondary endpoint will be analyzed. The secondary endpoint will be tested at a two-sided 0.05 significance level.

7.6.2.1 Sustained clinical response of RBX2660 vs. Placebo.

The null hypothesis of interest is that the rates of sustained clinical response (i.e., the rate of CDI occurrence with treatment success of the presenting CDI recurrence and no new CDI episodes for greater than 8 weeks after completing a blinded study treatment) are the same between the RBX2660 group and the Placebo group during the 6 months of follow-up. The alternative is that there is a difference in sustained clinical response rates. A Pearson's chi-square test will be used to test the null hypothesis that the response rate in the treatment group is equal to that of the control group. In addition, two-sided 95% confidence intervals for the difference in response rate between arms will be calculated using a normal distribution approximation. The null hypothesis will be rejected at the two-sided 0.05 significance level. Subjects who were deemed a Treatment Success for the efficacy analysis and exited prior to their 6 month follow-up will be conservatively counted as a sustained treatment failure for the purpose of this analysis.

An analysis of time to CDI occurrence after completion of the assigned blinded treatment will be analyzed and presented by the Kaplan-Meier procedure and median duration presented by days (and weeks) using the ITT, mITT, and PP populations. The estimates will be presented for each of the time points at which CDI recurrence assessments are scheduled to occur. A graphic presentation of the Kaplan-Meier estimates will supplement the tabular presentation. Between group comparisons will be performed using the log-rank test.

Time to CDI occurrence is defined as the number of days from enema administration to first assessment indicating recurrence, for those subjects who were deemed Treatment Failures or Indeterminate. Randomized subjects who do not complete the assigned blinded treatment will be censored at Day 0. All subjects who are discontinued for any reason prior to the 6-month timepoint will be censored at the last assessment date at/prior to Month 6. All subjects considered as a sustained treatment success will be censored at the date of their 6-month assessment.

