4.3 Method of Assignment of Subjects to Treatment Arms

After enrollment and confirmation of inclusion/exclusion criteria compliance, randomization occurs via the study database with blinded treatment occurring within 14 calendar days of randomization. The randomization assignment is transmitted only to the Rebiotix Operations Department, who will ship the correct IP to the site for each treatment. Subjects are considered enrolled once they sign the informed consent form.

Trained and authorized study personnel will access the centralized randomization system to randomize the subject to one of the available treatment arms. The randomization schedule will be created using randomized blocks within four strata based on antibiotics used at screening (Vancomycin alone, Vancomycin in combination, Fidaxomicin or Other), and randomized subjects will be assigned one of two treatments (Group A or Group B) within the appropriate

stratum. The randomization will not be stratified by site, so each site will draw from the same set of blocks. A subject will be assigned the next available treatment allocation from the randomization list. The randomization code and the date and time of randomization will be captured in the clinical database. Randomization will be in a 2:1 ratio with approximately 2 subjects randomized to active treatment for every 1 subject randomized to placebo.

Enrolled subjects who are exited prior to randomization or are randomized but exited prior to attempting the blinded treatment may be re-enrolled and thus randomized under a different subject identification numbers (re-randomized). If this occurs, they will be included in the analysis using their second randomization assignment and subsequent assessments and will only be counted once towards the total number randomized.

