4.4 Determination of Sample Size

To demonstrate a 69% success with one dose of the RBX2660 treatment group vs. 47% success in the Placebo control group, 240 subjects are required (power > 90%, nominal 2.5% type I error rate). Up to an additional 30 subjects will be enrolled to allow for a 10% loss-to-follow up rate, for a total of approximately 270 subjects. Considering the 2:1 randomization, this results in approximately 180 subjects in the RBX2660 arm and 90 subjects in the Placebo arm. Enrolled subjects who have signed consent and withdraw for any reason prior to administration of the first blinded enema will be replaced without counting toward the sample size cap. Replacement subjects will be randomized to ensure proper blinding.

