7.6.1.2 Sensitivity Analysis for the Primary Efficacy Endpoint

The primary efficacy analysis will be repeated using the ITT and PP population to assess the sensitivity of the primary endpoint regardless of the outcome of the mITT primary efficacy analysis. The ITT analysis will serve as the conservative analysis as it considers all subjects who exit prior to the 8-week efficacy assessment as treatment failures regardless of treatment failure documentation.

Three groups of sensitivity analyses will be performed to assess the sensitivity of the results to the borrowing of historical data from the previous Phase 2B study (Protocol 2014-01) of RBX2660.

- 1) A Pearson's chi-square test will be used to test the null hypothesis that the response rate in the treatment group is equal to that of the control group. In addition, two-sided 95% confidence intervals for the difference in response rate between arms will be calculated using a normal distribution approximation. This sensitivity analysis will be conducted using the mITT, ITT, and PP populations using data from the 2017-01 study only.
- 2) Sensitivity of the primary analysis (Bayesian analysis) to the analysis population (ITT, PP) using Bayesian analysis.
- 3) Sensitivity of the primary analysis (Bayesian analysis) to the following different sensitivity analysis populations from the 2014-01 study using Bayesian analysis. The **2014-01 Sensitivity Analysis Population #1** represents the ITT population from the 2014-01 study, and the **2014-01 Sensitivity Analysis Population #2** represents the

population used for the primary analysis inclusive of one subject in Group C who was exposed to product but did not receive the full enema.

2014-01 Sensitivity Analysis Population #1				2014-01 Sensitivity Analysis Population #2			
2014-01 Treatment Group	# Subjects	# Responders	Response Rate	2014-01 Treatment Group	# Subjects	# Responders	Response Rate
A	45	25	0.556	A	41	25	0.610
B	44	19	0.432	B	44	19	0.432
C	44	25	0.568	C	43	25	0.581

Efficacy analysis will be repeated without the borrowing of historical data from the Phase 2B study (Protocol 2014-01) using the mITT, ITT, and PP populations.

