An analysis of time to CDI recurrence after completion of the assigned blinded treatment will be analyzed and presented by the Kaplan-Meier procedure and median duration presented by days (and weeks) using the ITT, mITT, and PP populations. The Kaplan-Meier estimate of the median time (days) and the associated 95% confidence interval will be presented for each treatment group. A graphic presentation of the Kaplan-Meier estimates will supplement the tabular presentation. Between group comparisons will be performed using the stratified log-rank test based on the stratification factor at randomization. The corresponding hazard ratio of the treatment effect along with the 95% confidence interval will be calculated using a Cox proportional hazard model with treatment and the stratification factor at randomization as explanatory variables.

Time to CDI recurrence is defined as the number of days from enema administration to first assessment indicating recurrence for those subjects who were deemed Treatment Failures with CDI recurrence. All subjects who are Indeterminate or discontinued for any reason prior to assessment of efficacy will be censored at the last assessment date at/prior to Week 8. For the analysis of Time to CDI recurrence within 8 weeks, all subjects considered as a treatment success will be censored at the date of their 8-week assessment. For the analysis of Time to CDI

recurrence through 6 months, all subjects considered to have achieved sustained clinical response will be censored at the date of their 6-month assessment.

Finally, the sensitivity of the primary efficacy endpoint will be assessed in a multivariate logistic regression adjusting for possible interactions of the following covariates with treatment group: age (< 65 years, \geq 65 years), sex (Female, Male), race group (White, Non-white), ethnicity (Hispanic-Latino, not Hispanic-Latino), site geography (outside the US, Eastern US*, Southern US*, Northern US*, Western US*), randomization strata (i.e., treatment received at the qualifying event) and number of previous episodes of CDI recurrence at baseline. Other baseline variables will be compared for balance using the appropriate statistical test. This analysis will be performed on all analysis populations where at least 20 subjects in each sub-group are available for analysis to fully understand the observed treatment effect.

*States included in the identified US geographical regions are as follows:

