8.2 Adjustments for Covariates

Adjustments for covariates will be made in sensitivity analyses of the primary endpoint if applicable due to imbalance of a particular covariate.

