In this example, the first interim analysis occurs when 180 subjects have been enrolled. The observed control rate is 0.5, somewhat higher than seen in the Phase 2b trial. Example 3.1 shows the status of the trial at the first interim

[figure not shown]
Example 3.1: Status of the trial at the 1st interim

The posterior estimate of the control response rate (0.473) is somewhat lower than

[figure not shown]
observed due to the borrowing and the posterior probability of a treatment effect is insufficiently high to declare success at the first interim.

Example 3.2: Status of the trial at the 2nd interim

At the second interim (N=220, shown in Example 3.2), the observed response rates in both arms have been reduced. The trial has not shown sufficient evidence to declare success or futility and continues enrollment, though the predictive probability of success at the final analysis remains optimistic (0.797).

Example 3.3: Status of the trial at the final analysis

The final analysis is conducted when 270 patients have completed follow-up and 260 subjects qualify for the mITT population (Example 3.3). The single trial success criteria is updated to 0.99931, using the information fraction and 0.99943 criteria at the first two interims (0.692 and 0.846) to ensure an overall α –spend of 0.00125. The trial is declared a success at the 0.025 level, though it does not meet the single trial success criteria.

Performance Characteristics

The performance characteristics of the design were determined through trial simulation. We assume several scenarios for the underlying response probability for the control and treatment arms, considering control probabilities in $\{0.2, 0.3, 0.4, 0.45, 0.5, 0.6, 0.7\}$ and additive treatment effects of $\{0.0, 0.05, 0.1, 0.15, 0.2, 0.25, 0.3\}$. The scenario with a control probability of 0.45 and a treatment effect of 0.15 corresponds most closely to what was observed during the Phase 2b trial. The scenarios with treatment effects of 0 correspond to null scenarios. For the purposes of simulation, we assume that patients are randomized in 3 patient blocks, that interim analysis were performed with exactly 160 and 220 subjects completed, and that the 270 mITT subjects have complete data at the final analysis.

Operating Characteristics

We simulated 1,000,000 virtual trials for each scenario. The results of the simulations are summarized using the following operating characteristics.

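### Randomization is stratified by screening antibiotic, but the confirmatory 6-month tests in SAP 7.6.2.1 are unstratified and conflict with the stratified log-rank in SAP 7.6.1.2 (minor)

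*SAP*

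**What the plan says.** **Randomization.** SAP 4.3, in line with Protocol 6.6: "The randomization schedule will be created using randomized blocks within four strata based on antibiotics used at screening". The strata are vancomycin alone, vancomycin in combination, fidaxomicin, and other. Allocation is 2:1.

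**Secondary endpoint.** SAP 7.6.2.1 compares sustained clinical response by a Pearson test at two-sided 0.05, with a normal-approximation interval for the difference. For the 6-month time to CDI occurrence it adds: "Between group comparisons will be performed using the log-rank test". No stratum is named.

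**Check without borrowing.** SAP 7.6.1.2, item 1, uses 2017-01 data only: a Pearson "chi-square test will be used to test the null hypothesis that the response rate in the treatment group is equal" to that of control, again with an unstratified interval.

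**Where the strata are used.** SAP 7.6.1.2 plans a "stratified log-rank test based on the stratification factor at randomization" for time to CDI recurrence and a Cox model with treatment and the stratification factor. The same section gives separate censoring rules for the 8-week and the 6-month versions of that analysis. It also lists a logistic regression of the primary endpoint whose covariates include the randomization strata, age (cut at 65) and number of previous episodes.

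**General rule.** SAP 8.2: "Adjustments for covariates will be made in sensitivity analyses of the primary endpoint if applicable due to imbalance of a particular covariate".

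**The concern.** An analysis should normally reflect the way subjects were randomized. Balancing the arms within strata removes part of the chance variation between them. A pooled test still counts that variation in its standard error, so when the strata predict outcome it rejects too rarely under the null and loses some power.

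There is also a plain inconsistency. The 6-month log-rank is stratified in one section and unstratified in another, so the same comparison could be reported with two p-values and no rule for choosing between them. The choice of log-rank matters more because SAP 6.4.2 describes the secondary endpoint as a time-to-event comparison and powers it by log-rank, while 7.6.2.1 leads with a chi-square. Finally, 8.2 makes adjustment depend on an imbalance seen in the data, whereas 7.6.1.2 lists its covariates without that condition.

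**Working it through.** **1. Reproduce the plan's figures.**

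*8-week endpoint (SAP 4.4: 69% v 47%, 240 subjects, power above 90%).* At 2:1 this is 160 and 80 subjects. The pooled rate is (160×0.69 + 80×0.47)/240 = 0.617. Null standard error: √(0.617×0.383×(1/80+1/160)) = 0.0666. Alternative standard error: √(0.47×0.53/80 + 0.69×0.31/160) = 0.0667. Power = Φ((0.22 − 1.96×0.0666)/0.0667) = 91.0%. This agrees.

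*Log-rank (SAP 6.4.2: 104 per arm, exponential, 99.5%).* Hazard ratio = ln 0.69/ln 0.47 = 0.491. Taking 6 months as 180/56 = 3.214 eight-week periods, event probabilities are 1 − 0.69^3.214 = 0.697 and 1 − 0.47^3.214 = 0.912. Events = 104×(0.697+0.912) ≈ 167. Power = Φ(√(167/4)×0.710 − 1.96) = 99.6%. At the trial's 2:1 split (160:80, about 184 events, factor 2/9) it is 99.5%. This agrees.

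**2. Why the pooled test is conservative.** Let R² be the between-stratum variance of the success rate divided by p(1−p). With balance within strata, the true variance of the difference is about (1−R²) times the variance the pooled test uses. Its size is then about 2Φ(−1.96/√(1−R²)).
- R² = 0: 0.050.
- R² = 0.016: 1.96/√0.984 = 1.976, size 0.048.
- R² = 0.062: 1.96/√0.938 = 2.024, size 0.043.

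**3. Simulation, Pearson v CMH.** The documents give no stratum sizes and no stratum-specific rates, so both are assumed. OR is the largest odds ratio of success between strata. N=240, blocks of 3 within strata (the SAP appendix's own simulations say "we assume that patients are randomized in 3 patient blocks"), two-sided 0.05, 400,000 trials per row, overall rates held at the stated values. The 60% v 45% case matches the scenario that the appendix calls closest to Phase 2b (control 0.45, effect 0.15). The 8-week rates stand in for sustained-response rates, which the plan does not give.

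| Stratum shares (%) | OR | R² | Size: Pearson / CMH | Power 69 v 47: Pearson / CMH | Power 60 v 45: Pearson / CMH |
|---|---|---|---|---|---|
| 60/10/25/5 | 1 | 0.000 | 0.0503 / 0.0497 | 91.07 / 90.96 | 60.09 / 59.71 |
| 60/10/25/5 | 2 | 0.011 | 0.0496 / 0.0503 | 91.25 / 91.32 | 59.92 / 59.98 |
| 60/10/25/5 | 4 | 0.043 | 0.0449 / 0.0493 | 91.43 / 91.96 | 60.14 / 61.46 |
| 40/20/25/15 | 2 | 0.017 | 0.0483 / 0.0496 | 91.33 / 91.49 | 59.99 / 60.28 |
| 40/20/25/15 | 4 | 0.066 | 0.0428 / 0.0499 | 91.80 / 92.59 | 60.27 / 62.40 |
| 85/2/8/5 | 2 | 0.004 | 0.0495 / 0.0497 | 91.20 / 91.13 | 60.16 / 59.91 |
| 85/2/8/5 | 4 | 0.017 | 0.0487 / 0.0501 | 91.25 / 91.40 | 60.27 / 60.49 |
| 25/25/25/25 | 2 | 0.016 | 0.0483 / 0.0496 | 91.27 / 91.42 | 60.07 / 60.31 |
| 25/25/25/25 | 4 | 0.062 | 0.0432 / 0.0499 | 91.76 / 92.56 | 60.17 / 62.25 |

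In the equal-share rows, placebo success runs from 38% to 56% across strata at OR 2 and from 31% to 64% at OR 4.

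A further set of assumed strata gave Pearson sizes of 0.047-0.048 (OR 2) and 0.041-0.043 (OR 4), against about 0.049-0.050 for CMH. The CMH gains were about 0 to 0.3 points (OR up to 2) and 0.6-1.0 points (OR 4) at 69% v 47%, and 0.4-0.8 and 1.9-3.5 points at 60% v 45%. These are ranges over the cases tried, not bounds.

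**4. Simulation, log-rank.** N=240, 20,000 null and 8,000 power trials per case, shares 60/10/25/5 and equal. With a stratum hazard ratio of 2, size is 0.045-0.048 unstratified against 0.050-0.051 stratified. At 4 it is 0.030-0.037 against 0.049-0.053. The largest power gain is 99.86 − 99.48 ≈ 0.4 points.

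**The case against.** The strongest reply is that nothing here is invalid and little is lost. The pooled tests do not exceed 5%, power at the planned effect changes by a point or less up to OR 4, and the log-rank already has about 99.5% power. If antibiotic type does not predict recurrence, stratifying costs 0.1-0.4 points. All of this stands.

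It is also fair to say that the strata are not neglected. A reader might infer that only one 8-week analysis uses them. SAP 7.6.1.2 does not support that: it has the stratified log-rank, the stratum-adjusted Cox model, a logistic regression naming the strata, and a 6-month censoring rule. Likewise 8.2 might suggest that all adjustment is chosen after seeing the data, but the covariates in 7.6.1.2 are listed beforehand. The two sections need reconciling, no more.

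The reply is right on item 1 of 7.6.1.2 as well. That chi-square isolates the effect of borrowing, and the primary Bayesian model has no stratum term. Replacing it with CMH would change borrowing and stratification together. It should stay, with CMH added.

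The reply does not remove the conflict between the two log-rank specifications, or the mismatch between the randomization and the confirmatory chi-square.

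**Conclusion.** The point holds as a minor matter of efficiency and consistency. The confirmatory analysis in SAP 7.6.2.1 does not use the randomization strata, and its log-rank conflicts with the one in 7.6.1.2 for an overlapping 6-month comparison.

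The size of the effect rests entirely on assumed stratum shares and prognostic strength. With no association there is no conservatism. At OR 4 the chi-square's size is about 0.041-0.043 with well-spread strata and 0.045-0.049 when one stratum holds most subjects. The gain at the planned effect is then 1.0 point or less; it reaches 1.9-3.5 points only at the smaller 60% v 45% effect with well-spread, prognostic strata.

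Two stronger readings are not supported. One is that ignoring the strata inflates type I error; the error goes the other way. The other is that power is lost at the 0.99943 single-study threshold. That threshold belongs to the Bayesian primary analysis, while the secondary tests are at two-sided 0.05 and the no-borrowing chi-square has no success threshold.

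**What to change.** - **SAP 7.6.2.1:** replace the Pearson test with the CMH test stratified by the randomized antibiotic stratum, report a stratified risk difference with its confidence interval, and use the stratified log-rank as in 7.6.1.2, so that one specification governs the 6-month comparison.
- **SAP 7.6.1.2, item 1:** keep the Pearson test as the like-for-like check on borrowing and report the CMH result beside it.
- **SAP 8.2:** remove the imbalance trigger and refer to the covariates already listed in 7.6.1.2.
- **Sparse strata:** add no rule that merges strata according to observed outcomes. CMH does not need one, and such a rule would bring back a data-dependent choice.

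The cost is SAP wording before unblinding, with no extra data or subjects. The statistical downside is about 0.1-0.4 points of power if the strata turn out not to be prognostic.

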6.13. Unscheduled Possible Recurrence Visit

If CDI recurrence is suspected any time within 8 weeks of the last study enema due to documentation of three or more unformed/loose (i.e. Bristol Stool Scale type 6-7) stools within 24 or fewer consecutive hours for at least two consecutive days, possible treatment failure must be assessed. An in-office visit is required and the subject must provide a fresh stool sample to test for the presence of *C. difficile* toxin as defined by the protocol.

The following study activities/data will be collected at the Unscheduled Possible Recurrence visit:

- Collect fresh stool sample to send to the central laboratory for analysis
- Assess recurrence of CDI
- Vital signs: temperature, pulse, blood pressure, respiration
- Adverse event collection, including the new onsets of obesity, metabolic syndrome, pre-diabetes, diabetes and/or autoimmune disorders
- Changes to concomitant medications since last visit
- Cdiff32 health-related quality of life questionnaire
- Assess changes in medical history, including Charlson Comorbidity Index variables. Worsening of conditions are to be captured as an adverse event with appropriate source documentation. An improvement in a condition may not have physician diagnosis or source documents to support improvement; subject self-reported improvement in a condition does not require medical documentation to support the improvement.
- Assess for protocol deviations

- For subjects who consented to the Optional Stool Sample collection, remind the subject to collect and ship a stool sample to Rebiotix.

Treatment failure (CDI recurrence) is defined as:

- The presence of CDI diarrhea within 8 weeks of administration of a study enema, which includes a positive stool test for *C. difficile* toxin at the time of the diarrhea using the study required *C. difficile* testing algorithm.

[figure not shown]
To ensure consistency across clinical sites for the determination of study failure, the central laboratory will perform the required C. DIFF QUIK CHEK COMPLETE® Test (QCC Test) rapid enzyme immunoassay test for glutamate dehydrogenase (GDH) and toxins A and B.

In the case of suspected treatment failure where there is an immediate concern for subject safety, including the potential for serious adverse events, a C. DIFF QUIK CHEK COMPLETE® Test will be permitted to be conducted at the site or other laboratory known to the site **in addition to** sending a sample to the central laboratory for testing.

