8.1. Assessment of Efficacy

The primary efficacy parameter is treatment success, defined as the absence of CDI diarrhea through 8 weeks after completing a study treatment. Efficacy assessments will occur at the 1-, 4- and 8-week office visits.

Recurrence of CDI after 8 weeks from completion of the assigned study treatment is considered a new *C. difficile* infection, as defined by the Centers for Disease Control (CDC website http://www.cdc.gov/hai/eip/cdiff_techinfo.html; published August 30, 2012; accessed October 02, 2016).

Primary Efficacy Endpoint: Recurrence of CDI within 8 weeks of blinded treatment.

The primary efficacy analysis will be performed on all pre-defined analysis populations comparing the RBX2660 arm to the Placebo arm, Intent-to-Treat (ITT), modified Intent-to-Treat (mITT) and Per-Protocol (PP). However, the determination of meeting the pre-defined primary efficacy endpoint will utilize the mITT population results. The primary analysis of the study will be a Bayesian hierarchical model, which formally incorporates data from a previous randomized Phase 2b study (Protocol 2014-01) of RBX2660. This analysis will demonstrate the efficacy of RBX2660 by showing a sufficiently high posterior probability that the rate of success in the treatment group is superior to the rate of success in the control group. Secondary efficacy endpoints will also be completed on all analysis populations. Finally, all safety analyses will be performed on the Safety

population (SP) which includes all subjects in whom a blinded enema was at least opened and attempted.

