solicited events from the date of enrollment to the 1-week follow-up visit after receiving the blinded study enema. The diary will be collected and reviewed at the baseline visit prior to blinded enema administration, and then collected and reviewed at the 1-week follow-up visit following enema administration.

Subjects who are deemed failures following the blinded treatment per the pre-specified treatment failure definition may elect to receive an unblinded RBX2660 enema. The unblinded enema is to be administered within 21 calendar days of failure determination. If a subject has a CDI episode on-study and the treatment plan is to pursue a treatment other than that specified in the protocol, the subject will be exited prior to receipt of the non-study treatment (ex. fecal microbiota transplant).

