4.1.3 Treatment Failure

Treatment failure (CDI recurrence) is defined as:

- The presence of CDI diarrhea within 8 weeks of administration of a study enema; which includes a positive stool test for *C. difficile* toxin at the time of the diarrhea.

To ensure consistency across clinical sites for the determination of study failures, the central laboratory will perform the required C. DIFF QUIK CHEK COMPLETE® Test rapid enzyme

immunoassay for glutamate dehydrogenase (GDH) and toxins A and B. If the test is inconclusive, the central laboratory will conduct a second confirmatory test by PCR.

In the case of suspected treatment failure where there is an immediate concern for subject safety, including the potential for serious adverse events, a C. DIFF QUIK CHEK COMPLETE® Test will be permitted to be conducted at the site or other laboratory known to the site in addition to sending a sample to the central laboratory testing. If the C. DIFF QUIK CHEK COMPLETE® Test is not available, a testing algorithm that directly assesses the presence of *C. difficile* toxin for laboratory confirmation of recurrent CDI should be used. In the event, the test results from the central laboratory differ from that of a local laboratory, the results from the central laboratory will be used in determination of treatment failure. For subjects who are suspected of treatment failure, but for whom there is not a test result from the central laboratory for the suspected episode, a deviation will be entered to the database, and due documentation of the subject's symptoms and all available treatment and outcome data will be sent to the Endpoint Adjudication Committee (EAC) for blinded, independent adjudication of treatment outcome.

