6.4.2 Secondary Efficacy Endpoint

The secondary efficacy endpoint is the recurrence of CDI through 6 months after blinded treatment. This will be analyzed as the difference in time to CDI event between RBX2660 and Placebo following blinded treatment through 6 months of follow-up. This analysis will only be

analyzed if statistical significance ($p < 0.05$) is demonstrated for the primary efficacy endpoint. These endpoints will be tested at a two-sided 0.05 significance level.

The null hypothesis of interest is that there is no difference between RBX2660 and Placebo treated subjects in the probability of CDI at any time point during the 6 months of follow-up. The alternative is that there is a difference in the probability of CDI at any time point during 6 months of follow-up.

The power to detect the difference between RBX2660 and Placebo treatment at 6 months was estimated by 10,000 simulations of time to event data, with 104 subjects per treatment group. The data was simulated assuming the exponential distribution with the rate parameter lambda estimated using the 8-week success rates of 69% and 47% for RBX2660 and Placebo, respectively. Using the log-rank test, the power to detect the difference between the two groups at 6 months was 99.5%.

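### The 6-month time-to-CDI analysis has no event rule for CDI after week 8, censors exits caused by CDI, and treats Indeterminate subjects in two opposite ways

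*SAP*

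**What the plan says.** - SAP 6.4.2 describes the secondary endpoint as CDI through 6 months after blinded treatment, analysed as a difference in time to CDI. Its only power statement is for that analysis: "Using the log-rank test, the power to detect the difference between the two groups at 6 months was 99.5" per cent. It assumes 104 subjects per group and exponential times with rates taken from 8-week success of 69% and 47%.
- SAP 7.6.2.1 runs the event time to the "first assessment indicating recurrence, for those subjects who were deemed Treatment Failures or Indeterminate". It adds: "All subjects who are discontinued for any reason prior to the 6-month timepoint will be censored at the last assessment date at/prior to Month 6". Sustained treatment successes are censored at their 6-month assessment.
- SAP 4.1.3 defines Treatment Failure as "The presence of CDI diarrhea within 8 weeks of administration of a study enema". Protocol 8.1 separates later episodes: "Recurrence of CDI after 8 weeks from completion of the assigned study treatment is considered a new" *C. difficile* infection.
- SAP 4.1.2 defines sustained clinical response as week-8 success plus no new CDI episode afterwards.
- SAP 7.6.1.2 also includes a 6-month time-to-recurrence analysis. Its events are Treatment Failures only, and it says: "All subjects who are Indeterminate or discontinued for any reason prior to assessment of efficacy will be censored".
- SAP 4.1, on a subject whose on-study CDI is to be treated outside the protocol: "the subject will be exited prior to receipt of the non-study treatment". Protocol 3.8 keeps treatment failures who do not take the open-label enema on their original schedule.
- SAP 7.6.2.1 also specifies a Pearson chi-square test of the sustained response rate. There, week-8 successes who exit before month 6 count as failures.

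**The concern.** The secondary objective adds one thing to the primary: what happens between week 8 and month 6. The time-to-event rule does not say what to do with a CDI episode in that period. A subject who succeeds at week 8, has CDI at month 4 and completes follow-up is not a Treatment Failure, not a sustained success and not discontinued. Whoever programs the analysis must invent the rule.

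Two further rules distort the same analysis. If the late episode leads to exit under SAP 4.1, the event becomes a censoring, and it is informative because the exit was caused by the outcome. Indeterminate subjects enter as events in one section and as censored in the other, so the two 6-month time-to-CDI analyses in the SAP can disagree for reasons unrelated to the data.

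At stake is whether this analysis can show waning of effect, and whether its stated power describes the analysis that will be run.

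**Working it through.** **Inputs.** From SAP 6.4.2: 8-week success 69% (RBX2660) and 47% (placebo), exponential times, 104 per group, log-rank test, two-sided 0.05, stated power 99.5%. From SAP 4.4: 2:1 allocation, about 180 and 90. From Protocol 1.5.2: 91 of 95 subjects successfully treated with RBX2660 still CDI-free, at a mean follow-up of 8.2 months. Six months is taken as day 180 (SAP 6.2.2) and week 8 as day 56.

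**Step 1: reproduce the stated power.**
- Daily hazards: −ln(0.69)/56 = 0.00663 and −ln(0.47)/56 = 0.01348. Hazard ratio 0.491.
- CDI-free at day 180: 0.69^(180/56) = 0.303 and 0.47^(180/56) = 0.088.
- Expected events: 104 × (0.697 + 0.912) = 167.
- Schoenfeld: Φ(|ln 0.491| × √(167.3/4) − 1.96) = Φ(2.63) = 99.6%. Simulation (50,000 runs): 99.6%.

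The stated 99.5% reproduces when every CDI event to day 180 is counted.

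**Step 2: apply the literal event rule.** Only CDI by day 56 is an event.
- Expected events: 104 × (0.31 + 0.53) = 87.
- Schoenfeld: Φ(|ln 0.491| × √(87.4/4) − 1.96) = Φ(1.36) = 91.3%. Simulation: 90.6%.
- Events dropped: (167.3 − 87.4)/167.3 = 48% overall, 55% on RBX2660 and 42% on placebo.

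The literal rule does not reproduce 99.5%, so the SAP's own power calculation assumes that late CDI is an event.

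**Step 3: repeat at about 180/90.** With late CDI counted: 207 events, 99.9% power. Not counted: 180 × 0.31 + 90 × 0.53 = 103.5 events, 94.6% power (simulation, 10,000 runs each).

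**Step 4: vary the late rate.** The constant hazard after week 8 is the SAP's assumption. The only late rate in the documents is 4/95 = 4.2%, in RBX2660-treated subjects only. Applying it to placebo, and the 10% and 20% values, are assumptions. Late CDI is given as a share of week-8 successes; allocation is 180/90.

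| Late CDI, RBX2660 / placebo | Power, late CDI counted | Power, not counted |
|---|---|---|
| 4.2% / 4.2% | 93.6% | 94.7% |
| 10% / 10% | 91.8% | 94.8% |
| 20% / 20% | 88.5% | 94.4% |
| 20% / 4.2% | 60.8% | 94.6% |

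The differences within the last column are simulation noise, since late CDI does not enter it. In the last row the true 6-month CDI-free rates are 0.69 × 0.80 = 55% and 0.47 × 0.958 = 45%, but the literal curves would stay at 69% and 47%.

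**The case against.** The strongest reply is that the same section contains a test without this gap. The chi-square in SAP 7.6.2.1 counts a new CDI episode as non-response and an early exit of a week-8 success as failure, and the rejection rule stands with that test. This is correct. A reader might infer that the trial could report sustained protection whatever happened after week 8; the documents do not support that. What remains is that SAP 6.4.2 names the time-to-event comparison as the secondary analysis and rests its power statement on it.

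Second, late CDI is left without a rule, not expressly excluded. Only sustained successes are censored at month 6, and estimates are to be shown at each scheduled CDI assessment, so late CDI was probably meant to be an event. That stands, but the event sentence does not say so.

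Third, a reader might infer that late CDI goes unobserved. The required visit is indeed limited: "If CDI recurrence is suspected any time within 8 weeks of the last study enema". But the month 3 and 6 calls assess CDI (Protocol Table 6-1 and 6.12), the CDI diarrhea definition in Protocol 3.4 applies throughout the study, and the EAC's scope is deferred to a charter not among the documents. Confirmation after week 8 is weaker, not absent. Extending visits and central stool testing to month 6 would be an added procedure, which this point does not require.

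Fourth, exit is not automatic. SAP 4.1 gives only fecal transplant as its example, and the restriction on CDI antibiotics in Protocol 5.6 runs only to the 8-week assessment.

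Finally, one might infer that with about 7 late episodes (4.2% of 180 × 0.69 + 90 × 0.47 = 166.5) a few misclassified ones would decide the result. At the SAP's rates they would not: 124/180 against 42/90 gives chi-square p = 0.0004, and moving all 7 to failure on RBX2660 (117/180) still gives p = 0.004.

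**Conclusion.** The concern holds for the 6-month Kaplan-Meier and log-rank analysis. As worded, it gives late CDI no event, turns a CDI-related exit into a censoring, and contradicts SAP 7.6.1.2 on Indeterminates. Because Indeterminate is undefined, it cannot be said whether those subjects would be false events.

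On the SAP's exponential model at 104 per group, the literal rule loses 80 of 167 expected events and lowers power from 99.6% to about 91%. That size depends on the constant hazard after week 8. At the Phase 2b late rate in both arms, counting late CDI or not changes power by about one percentage point. The more lasting defect is that, read literally, the analysis cannot show waning at any late rate.

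The point does not extend to the chi-square test of sustained response. SAP 6.4.2 and 7.6.2.1 do not agree on which test carries the secondary claim, and the weight of this point depends on how that is settled.

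**What to change.** 1. In SAP 7.6.2.1 and the 6-month part of 7.6.1.2, define the event as the first CDI episode meeting the protocol definition from the blinded enema through month 6, whether a Treatment Failure by week 8 or new CDI after it.
2. Define Indeterminate and handle it the same way in both sections: censor, as 7.6.1.2 already does.
3. Count an exit because of a CDI episode as an event on the episode date. This matches the mITT rule in SAP 6.3.2, which counts CDI-related exits before week 8 as failures. Keep censoring for other exits.
4. Restate the 6-month power under this rule and the 2:1 allocation. At 180/90, the SAP's constant hazard gives 99.9%, and the Phase 2b late rate applied to both arms gives about 93.6%.
5. Send reported CDI diagnoses after week 8 to the existing EAC.
6. Reconcile the exit sentence in SAP 4.1 with Protocol 3.8.

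The cost is wording in two SAP sections, one rerun of the power simulation, a line in the EAC charter, and the reconciliation in item 6. At the Phase 2b rate the EAC would see about 7 additional confirmed episodes. No visit or sample is added. The wording should be settled before any unblinded analysis, because the primary analysis takes place at week 8, while 6-month follow-up is still running.
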